2 ABBREVIATIONS USED IN THE PROTOCOL

3 ABSTRACT

We propose an Interventional Study of the effects of Geisinger's Fresh Food Farmacy program on patient health. In particular, we will conduct a pragmatic, prospective, randomized-controlled trial of Geisinger's Fresh Food Farmacy (FFF) program.¹

In July 2016, Geisinger began piloting the "Fresh Food Farmacy" (FFF) program for diabetic, food insecure patients in northeastern Pennsylvania. Fresh Food Farmacy brings a "food-asmedicine" approach to communities to combat high rates of obesity, pre-diabetes, and diabetes. The program evolves over time, but the key elements include the following. Participants receive a referral to the Fresh Food Farmacy dietitian who provides a diet prescription for fresh food for themselves and their household, enough for 5 days a week, 2 meals a day. Participants also receive medication management services from a pharmacist, and receive case management services from a health manager or other health care professional. Their biometric measures (HbA1c, fasting glucose, weight, BMI, blood pressure, total cholesterol, LDL cholesterol, and triglycerides) and medication usage are tracked on a regular basis. In addition, participants receive a comprehensive suite of services, including diabetes wellness classes; dietary

consultations; workshops to discuss challenges to healthy eating and diabetes management; selfmanagement training (including monthly group classes); cooking expos; and a welcome kit with measuring cups/spoons, recipes, and nutritional and program information.

FFF has received considerable attention, as it uses a holistic approach to address a key "social determinant of health" and providers, public health officials, and payers are increasingly willing to consider innovative approaches to improve the health of patients. While the potential to benefit patients is high, there is a need for randomized-controlled trial evidence for such programs to establish their effectiveness.

Geisinger plans to expand the program in the coming months, first in Scranton and then in Lewistown. The program faces capacity constraints such that the program cannot be offered to all eligible participants on the first day. We propose a pragmatic, randomized controlled trial as a way to implement the expansion of the program by randomizing eligible participants to receive the program at the start of the expansion, while those randomized to control will receive the program six months later. Such a structured roll out will allow a rigorous examination of the effects of the program for outcomes at 6 months, and for longer-term outcomes to the extent that effects take time to become apparent. The advantage of this approach is that we can rigorously test the effects of the program to learn whether it should be further expanded at Geisinger, attempted at other healthcare systems, or whether new approaches should be considered instead.

4 BACKGROUND AND SIGNIFICANCE

Diet, Chronic Disease, and Food Insecurity

In the past century, changes in diet and lifestyle have led to a dramatic increase in chronic dietrelated disease; today, almost half of all American adults have one or more preventable chronic diseases that are related to poor diet, such as cardiovascular disease, high blood pressure, and Type 2 diabetes.² These chronic diet-related diseases are collectively the #1 cause of death in the US, with over 800,000 deaths annually.³

One diet-related chronic disease of particular concern is Type II diabetes, the prevalence of which has increased from less than 1% in 1958 to 7.4% in 2015.⁴ In 2015, 23.3 million

IRB NUMBER: 2018-0297 IRB Approved: 02/24/2020

[figure not shown]
Americans were diagnosed with diabetes, and an estimated 7.2 million have diabetes but remain undiagnosed; diabetes is the #7 cause of death in the U.S. (24.7 per 100,000 persons), and treatment of diabetes was estimated to cost \$245 billion in 2012.5

Another consequence of the American diet is that obesity has risen at an unprecedentedly rapid rate. Since 1980, the prevalence of adult obesity in the United States has more than doubled,⁶ and as of 2015–2016, 39.8% of adults are obese,⁷ a level that the U.S. Surgeon General described as "epidemic".⁸ Obesity represents a serious public health problem, raising the risk of Type II diabetes, cardiovascular disease, cancer, and asthma.⁹ Obesity raises health care costs by \$2,741 annually per obese adult; for the U.S. as a whole, this amounts to \$190.2 billion per year, or 20.6% of national health expenditures.¹⁰ Obesity is responsible for roughly 365,000 deaths per year in the U.S.¹¹

The problem with the modern, Western diet is that it includes too much saturated fat, cholesterol, added sugars, sodium, and refined grains, and too little fresh fruits and vegetables and whole grains.¹² It is estimated that following a healthy diet could more than halve mortality from dietrelated chronic diseases and could improve other measures of health in clinically meaningful ways.¹³ For example, Sacks et al. (2001) find that the "DASH" diet (which contains large amounts of fresh fruits and vegetables) and low-sodium intake reduced systolic blood pressure by 11.5 mm Hg in participants with hypertension.¹⁴ LDL cholesterol can be expected to fall by 10% with a healthier diet.¹⁵ Sargrad et al. (2005) find that high-protein or high-carbohydrate diets that lead to weight loss among type 2 diabetic patients are associated with a 1.3% reduction in Hemoglobin A1c concentrations.¹⁶

There are many possible explanations for the low-quality Western diet, but for lower-income individuals a possible contributing factor is food insecurity, which is defined as the limited or uncertain availability of nutritionally adequate food.¹⁷ This could be due to low income or low access/availability of healthy food sources. Historically, food insecurity was associated with being underweight or stunted, but in the modern food environment, food insecurity can cause

CONFIDENTIAL AND PROPRIETARY

and/or coexist with obesity and Type II diabetes.¹⁸ Approximately 1 in 4 Americans with cardiometabolic conditions that lead to cardiovascular-related death, such as hypertension, hyperlipidemia, and diabetes, experience "food insecurity" (i.e. difficulty accessing or affording nutritious food).¹⁹

Despite the consensus that addressing diet and food insecurity is an important way to improve health, there remains considerable uncertainty over the effectiveness of various approaches. We propose to conduct an RCT to evaluate the "Fresh Food Farmacy," an innovative approach that addresses food insecurity through the health care system. This is in line with other programs that are being studied that follow a food-as-medicine approach.²⁰

Specific Details:

Disease/diagnosis: Type II diabetes

Population to be studied: Food-insecure patients of Geisinger

Endpoints: HbA1c; fasting glucose; weight, BMI; blood pressure; total cholesterol, LDL

[figure not shown]
cholesterol, triglycerides (lipid panel); and healthcare utilization.

Rationale for the proposed project

In July 2016, Geisinger began piloting the "Fresh Food Farmacy" (FFF) program for diabetic, food insecure patients in central Pennsylvania. The program brings a "food-as-medicine" approach to address a key social deterimant of health for these patients. Patients are eligible for the Fresh Food Farmacy program if they meet the following criteria:

- 1. Type II Diabetes and an HbA1c \ge 8.0% as determined in Geisinger EMR
- 2. Food insecure based on a two-question survey instrument
- 3. Age ≥ 18 and age ≤ 85
- 4. Living within geographic reach of the program

A Fresh Food Farmacy dietitian prescribes fresh food for meals five days per week for each patient's family. Prescriptions are filled at no charge at a local clinic. Complementary services include case management, wellness and cooking classes, recipes to use the fresh food, medication management, self-management training (including monthly group classes), and

biometric tracking. Fresh Food Farmacy staff collaborate with the patient's primary care provider to request and collect biometric measurements regularly (HbA1c and Lipid panel every 6 months). The full program is described here: https://www.geisinger.org/freshfoodfarmacy

Through random assignment to the start-date of the intervention, we plan to study the impact of the FFF program on these biometrics and downstream utilization.

FFF has received considerable attention, as it uses a holistic approach to address a key "social determinant of health" and providers, public health officials, and payers are increasingly willing to consider innovative approaches to improve the health of patients. While the potential to benefit patients is high, there is a need for randomized-controlled trial evidence for such programs to establish their effectiveness.

[figure not shown]
Geisinger plans to expand the program in the coming months, first in Scranton and then in Lewistown. The program faces capacity constraints such that the program cannot be offered to all eligible participants on the first day. We propose a pragmatic randomized controlled trial as a way to implement the expansion of the program by randomizing eligible participants to receive the program at the start of the expansion (treatment group), while those randomized to the control group will receive the program approximately six months later. Such a structured roll out will allow a rigorous examination of the effects of the program for outcomes at 6 months, and for longer-term outcomes to the extent that effects take time to become apparent. The advantage of this approach is that we can rigorously test the effects of the program to learn whether it should be further expanded at Geisinger, attempted at other healthcare systems, or whether new approaches should be considered instead.

Existing evidence

Medically-tailored Meals

There is related research on "medically-tailored meals" (MTM) that are typically delivered to patients. This dramatically lowers the cost of consuming a nutritious diet, both in terms of time cost for acquisition and preparation as well as the direct monetary cost of healthy ingredients. The provision of nutritious food by health care providers is becoming increasingly common.²¹ These programs typically do not deliver a patient's entire nutritional intake. Rather, they are

CONFIDENTIAL AND PROPRIETARY

designed to provide a significant supplement each week, roughly half of the patient's intake. Meals are typically prepared under the supervision of a registered dietitian, so they are closely tailored to the nutritional recommendations for a patient's medical condition.

Little research has been conducted on the impact of such meal delivery to test whether the program improves health and is potentially cost effective. Gurvey et al. 2013 report an observational study that found reductions in costs among Medicaid managed care beneficiaries with life-threatening illnesses on the order of 31%.²² Berkowitz et al. 2017 conducted an observational study of the Community Servings program in Massachusetts that provides medically-tailored meals to patients with life-threatening illnesses resulting in large reductions in ED usage and inpatients stays and a 16% reduction in healthcare spending overall.²⁰

5 HYPOTHESIS AND SPECIFIC AIMS

5.1 Hypothesis

Our primary hypothesis is that the Fresh Food Farmacy program will improve patient health; specifically, we expect the program to result in significantly reduced levels of HbA1c, lower blood pressure, and fewer emergency department visits and inpatient admissions.

5.2 Specific Aim 1: Measure Effectiveness of FFF on clinical measures

Our first specific aim is to evaluate the effectiveness of FFF on clinical measures of health including HbA1c, fasting glucose, weight, BMI, blood pressure and lipid panel. HbA1c is glycated hemoglobin, a long-term measure of glucose in the blood that is used to classify individuals' diabetes status and to track management of diabetes. We will collect this information from the treatment and control groups in follow-up visits described below.

5.3 Specific Aim 2: Measure Effectiveness of FFF on healthcare utilization

Our second specific aim is to evaluate the effectiveness of FFF on healthcare utilization including ED visits and a combination of ED visits and inpatient admissions, as well as costs to Geisinger Health Plan. Direct utilization as part of the program will be considered as a

comparison to reductions in utilization after enrolling in the program. We plan to study program participants as well as their family members who are expected to benefit from the healthy food.

[figure not shown]
We will collect this information from administrative data from electronic health records and Geisinger Health Plan claims. These are additional health outcome measures and provide a way to consider the cost effectiveness of the program. Program data on the use of services by participants will be included for the full comparison of utilization. Our cooperation with Geisinger, which not only conducts the FFF program but also maintains records of medical care utilization, is a strength of this proposal. FFF also provides services for patients who are not Geisinger Health Plan members. Highmark (another local insurer) may share utilization data for their patients that are participating in the program in the future. As with Geisinger data, any Highmark data would be shared with MIT researchers under a DUA that would be submitted to the IRB under an amendment.

6 PRELIMINARY DATA

As proof of concept that was part of a quality improvement initiative at Geisinger led by PI [name] and analyzed by researchers at MIT, existing electronic health records of Fresh Food Farmacy participants were compared to diabetic patients living in Northumberland and Lackawanna counties. Outcomes included changes in HbA1c, blood pressure and weight for patients as well as ED and inpatient admissions to Geisinger facilities.

Because participation in the Shamokin pilot program was not randomly assigned, there is no preexisting control group. Instead, each FFF participant was matched to other Geisinger patients (who did not participate in FFF) based on age, sex, payer type, and baseline HbA1c, as well as the timing of HbA1c measurements. Estimates of regression models based on these matched data imply that participation in FFF was associated with a reduction in A1C of roughly one point 60-180 days after enrollment. This non-randomized data suggests that the FFF program may be beneficial on these dimensions, but the non-randomized nature of the data and limited power underscore the importance of studying the question with a randomized controlled experiment.

CONFIDENTIAL AND PROPRIETARY

This preliminary analysis has several limitations: a small sample of participants in Shamokin, the lack of random assignment, measurements of HbA1c and weight at different periods of time. However, despite the small sample and limited power there is a statistically significant reduction in A1c, which suggests that the FFF is a credible program and worth investigating further through a field RCT.

We intend to continue to work with this historical data to provide context for the RCT. Details below.

7 STUDY DESIGN- RETROSPECTIVE STUDY

7.1 Description

A retrospective analysis component will be included in this study to allow historical data already collected in the EHR to provide context for the prospective, RCT.

7.2 Study Population

[figure not shown]
7.2.1 Approximate Number of Subjects

For the historical data analysis for context, we will compare approximately 200 FFF participants in Shamokin to similar diabetic, non-FFF participant patients in Lackawanna, Mifflin, Juniata, and Northumberland counties. We will also study household members: those who share the same residential address. For this data-only portion of the research, approximately 20,000 patients are considered to find the matches and test robustness to the ways the matching is conducted.

There are 2 groups of subjects identified in this retrospective protocol:

- Group 1- Past and Current participants in the Shamokin FFF program.
- Group 2- Diabetic, non-FFF participant patients in Lackawanna, Mifflin, Juniata, or Northumberland counties. Patients will be matched based on observable characteristics including HbA1c, age, sex, and ZIP code with Group 1 participants (FFF Participants).

CONFIDENTIAL AND PROPRIETARY

7.2.2 Inclusion Criteria

Inclusion criteria for the retrospective study is consistent with the current FFF inclusion criteria:

- 1. Type II Diabetes and an HbA1c \ge 8.0% as determined in Geisinger EMR
- 2. Food insecure based on a two-question survey instrument
- 3. Age ≥ 18 & age ≤ 85
- 4. Living within geographic reach of the program (Shamokin) or comparison areas: Lackawanna, Mifflin, Juniata, or Northumberland counties.

7.2.3 Exclusion Criteria

In general, patients who satisfy the following criteria are excluded from the FFF program; however, some may be allowed to enroll on a case-by-case basis:

- 1. Not English speaking
- 2. On active chemotherapy
- 3. On hospice or palliative care
- 4. Active psychiatric disorder that would preclude participation in the program
- 5. Active medical disorder that would preclude participation in the classes, weekly clinic visits, and/ or result in a limited diet, including:
 - o Severe asthma
 - o Severe COPD
 - Colitis requiring steroid therapy
 - o Moderate to severe kidney dysfunction with metabolic disorders
 - Celiac disease
- 6. Resides in a facility which provides meals.

[figure not shown]
Inclusion and exclusion criteria applicable to program participants only; these criteria are not applicable to household members.

7.3 Study Date Range

Data are analyzed from January 1, 2015 to December 31, 2019.

7.4 Study Timeline

Planning and analysis will occur this year. We aim to prepare a manuscript this year and seek publication through the following year. Ongoing analysis in parallel with the prospective trial will augment the analysis of the RCT through 2021 as described below.

8 STUDY DESIGN- PROSPECTIVE STUDY

8.1 Description

This is a pragmatic, randomized, prospective research study. Qualifying subjects will be randomized 1:1 to receive either early participation in the FFF program (treatment group) or later participation (control group).

8.2 Study Population

8.2.1 Approximate Number of Subjects

[figure not shown]
Approximately 500 Geisinger subjects will participate in this study with about half assigned to the treatment group and about half to the control group. Approximately 2000 household members will be included in the data-only portion of the research.

There are 3 groups of subjects identified in this prospective protocol.

Group 1- Will be randomized to the treatment ("Begin Now") group for the FFF program. Subjects will be consented to join the FFF study prior to learning their program start date. They will join the FFF program right away when the program opens in their geographic area. Data will be collected during the first 12 months of subject participation and EHR and claims data may be analyzed for an additional 12 month follow-up period (24 months in total).

Group 2- Will be randomized to the control ("Begin Later") group for the FFF program. These subjects will be consented to join the FFF study prior to learning their program start date. They will join the FFF program approximately 6 months after the program opens in their geographic area. Data will be collected during the first 6 months of subject participation and used as control data for the study. EHR and claims data may be analyzed for an additional 12 month follow-up period (24 months in total from the start of the trial).

Group 3- Household Member data. Consented subjects will be asked for the names and dates of birth (DOB) of individuals living in their household who will be consuming food and benefiting from the FFF program. A waiver of consent is being requested in order to access health

information from the household members' medical records. EHR and claims data may be analyzed 24 months from the start of the trial by a household member.

8.2.2 Inclusion Criteria

The inclusion criteria for the RCT will mirror the FFF program's eligibility criteria:

- Type II Diabetes and an HbA1c ≥ 8.0 as determined in Geisinger EMR. The most recent HbA1c value within the past 12 months will be used to determine eligibility.
- 2. Food insecure based on a two-question survey instrument
- 3. Age \geq 18 and age \leq 85
- 4. Living within geographic reach of the program
 - a. Lewistown, PA
 - b. Scranton, PA

[figure not shown]
If the study is unable to reach its enrollment goal within 1 year, the HbA1c inclusion criteria for the study and program may be reduced to $\geq 7.5\%$.

Patients should meet the above clinical criteria and be of able mind and body to participate with the educational, consultative and food provisional services. In addition, patients should understand and speak English.

8.2.3 Exclusion Criteria

Patients who satisfy the following criteria will be excluded from the proposed trial, although some may be allowed to enroll in the program itself on a case-by-case basis:

- 1. Already enrolled in FFF in Shamokin
- 2. Not English speaking
- 3. On hospice or palliative care
- 4. Acute or chronic psychosis
- 5. Active medical disorder that would preclude participation in the classes, weekly clinic visits, or result in a limited diet, including:
 - Cancer; active treatment
 - o Steroid dependent asthma/ COPD/ emphysema
 - o Steroid dependent Colitis
 - Chronic Kidney Disease with GFR< 30 mg/mmol
 - Celiac disease
 - o Cirrhosis
 - Steroid dependent arthritis
- 6. Resides in a facility which provides meals

Inclusion and exclusion criteria are applicable to program participants only; these criteria are not applicable to household members.

8.2.4 Recruitment

Step 1. Subject identification

In consultation with the investigators, study staff will coordinate the outreach, which is similar to outreach planned for the program. With assistance from a Geisinger data broker, we intend to screen the EMR for eligible patients meeting criteria for age, diagnoses, HbA1c elevation \geq 8.0%, and food insecurity, which is expected to be included in the EHR by the time of program enrollment. In the event that this is not yet completed, we will screen patients for food insecurity digitally by MyGeisinger outreach, by phone or in person at a clinic visit.

[figure not shown]
Step 2. Outreach and Informed Consent

Once the patient is identified as eligible via EMR data pull, a study staff member will review the patient's chart to ensure that the patient does not have any exclusionary criteria and contact the patient via phone to determine whether the patient is willing and capable of participating. Study staff will describe the FFF program that is being introduced to their area and how participation will begin on a rolling basis over the coming months. Study staff will then describe the study and determine if the patient is interested in hearing more about it. For those interested in participating, the study will be explained in more detail and verbal informed consent will be requested. A recruitment script has been developed to ensure information regarding the program and study is conveyed accurately and consistently by research staff. Study staff will be aware of diabetes-related resources and usual care for diabetics in case questions arise. For patients who provide verbal consent, an information sheet describing the FFF study will be sent to the patient via mail.

Step 3. Randomization and program initiation

After the study enrollment procedures described in Step 2, study staff will consult a predetermined treatment group/control group assignment for the subject ID number. Study staff will schedule patients' initial program visit.

Those who decline consent to be in the study will enter the program in the (non-study) manner used by FFF. To distribute entry into the program in an equitable way, this continues to entail randomizing the start dates to begin at the time of initial intake or approximately six months later. These patients will be excluded from the data analysis, except for a comparison of their eligibility variables to place the study population in context.

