The FFF program provides food for the entire household. As a result, we are requesting data on household members as well. For the prospective study, household members are identified by the subject to ensure an accurate listing of household members who are actively benefiting from the program. Pulling data using the same address may lead to including household members who are not actively living in the residence (e.g. college student who is not living at home). FFF plans to ask members about their family members in the future, and this will be used to check the household record extraction as well. Data will be provided to MIT with an encrypted household identifier. While we will not have follow-up visits with family members, we aim to observe clinical measures as they appear in the electronic health record. Household IDs will facilitate this analysis.

The retrospective data analysis will include the same data as the prospective study; however, household members will be identified by a shared home address due to no patient contact.

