### 2. The intervention

In July 2016, Geisinger began piloting the Fresh Food Farmacy (FFF) program for food-insecure patients with diabetes in Shamokin, PA. Fresh Food Farmacy brings a "food-as-medicine" approach to treat these patients. Participants receive a referral to the Fresh Food Farmacy dietitian who provides a prescription for fresh food for the patient and everyone else in their household, enough for 2 meals per day, 5 days per week. (They do not provide 3 meals per day, 7 days per week because it is assumed that the households have other sources of meals, and the program wishes to minimize waste.) The program lasts indefinitely; there is no predetermined end date.

FFF participants receive education on how to use the food. This includes dietitian consultations, new recipes each week, and cooking classes. Next, the program expects, but does not compel, participants to attend diabetes self-management classes from a prominent program developed at Stanford University. Clinic staff include nurses who check whether

patients have received preventive care, such as eye and foot exams and influenza vaccination. Participants' biometric measures (HbA1c, fasting glucose, weight, BMI, blood pressure, total cholesterol, LDL cholesterol, and triglycerides) and medication usage are tracked on a regular basis. On a case-by-case basis, participants may receive cooking equipment to help in food preparation.

FFF has received considerable attention (e.g. Aubrey, 2017; Davidson 2017; Feinberg et al., 2017 and 2018), as it uses a holistic approach to address a key Social Determinant of Health (food insecurity), and because providers, public health officials, and payers are increasingly willing to consider such innovative approaches to improve the health of patients. Indeed, over 100 healthcare systems have consulted with Geisinger about their operation and are considering adopting it. Geisinger recognizes that a key next step is to allow for a randomized-controlled trial in order to accurately measure the effectiveness of the FFF program.

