Recruitment will be conducted over the phone; the program will be described, consent will be sought, and then patients will be randomized to either treatment ("start FFF now") or control ("start FFF later"). Note that all patients eligible for FFF, whether or not they agree to participate in the study, will be randomized to determine the timing with which they will enroll in FFF. This is the way the program is being introduced, akin to a lottery, and ensures that there is no incentive to refuse to participate in the study in order to start FFF sooner. Recruitment staff will discover whether the patient is randomized to start now or start later in a tamper proof REDCap application, which consults a randomized allocation table that the recruiter cannot access and a treatment status that is locked along with the patient's identifying information and study ID. The recruiter will then set up the patient's first appointment for those in the treatment group and will reach out to patients 5 months later to set up appointments for the group randomized to start later. We anticipate finding the patients 5 months later because all subjects are Geisinger Health patients, whose current address is on file, and we will ask for two other contacts at the time of recruitment.

The randomization is stratified using levels of HbA1c: <8.0 (in the event that the threshold is lowered),  $\geq$ 8.0 and <9.5, and  $\geq$  9.5 to attempt to ensure balance on a key pre-study control and because we are interested in estimating effects separately by these categories to inform

threshold setting in future applications. The randomization happens separately by location (Scranton and Lewistown) as well.

The trial will launch in April 2019 in Scranton, and likely June 2019 in Lewistown. We plan to continue enrollment until we attain at least 500 subjects (half in treatment) or when the recruitment period has lasted 2 years. If recruitment slows, we will consider lowering the eligibility threshold to an HbA1c of at least 7.5 rather than 8.0, and we may consider expanding the geographic limit.

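### Assignment is drawn per subject but the food goes to the whole household, and no rule limits a home to one subject, so some controls may receive the food component during their control window

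*Protocol*

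**What the plan says.** **Unit of assignment.** In Protocol 8.2.4, Step 3, "study staff will consult a predetermined treatment group/control group assignment for the subject ID number". The SAP (Enrollment & Randomization) describes an allocation table in REDCap and "a treatment status that is locked along with the patient's identifying information and study ID". Two factors structure the list: "The randomization is stratified using levels of HbA1c", and "The randomization happens separately by location (Scranton and Lewistown) as well". Household is not a factor.

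**Unit that receives the food.** Protocol 9.2.1: "The FFF program provides food for the entire household". SAP section 2: the dietitian gives "a prescription for fresh food for the patient and everyone else in their household". Protocol 5.3 expects family members to benefit.

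**Household information.** Protocol 8.2.1: "Consented subjects will be asked for the names and dates of birth (DOB) of individuals living in their household". Protocol 9.2.1 adds an encrypted household identifier in the analysts' data, intended for the analysis of relatives. The SAP (Enrollment & Randomization) notes that current addresses are on file.

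**What is absent.** Neither document limits a home to one subject, links the assignments of co-residents, or excludes a patient who lives with someone already in the program. The only exclusion for existing program exposure (Protocol 8.2.3) is enrolment at the Shamokin pilot site. The primary model (SAP section 4) has no household term and no clustering of standard errors.

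**The concern.** The SAP (section 2) bases the six-month comparison on a control group that has not started the program. That holds for a control's own enrolment. It need not hold for the food on the table if another person in the home is already a participant. Food insecurity is usually shared within a home, so two eligible people at one address are plausible. The Protocol expects about 2000 household members for about 500 subjects, roughly four each.

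Three analyses are touched.

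- **Primary intention-to-treat estimate.** Exposed controls shrink the contrast.
- **2SLS estimate.** Exposure is the subject's own months of engagement. A control fed through a housemate is coded zero, so the numerator shrinks while the first stage does not.
- **Spillover analysis.** A relative living with one treated subject and one control belongs to neither arm, and each co-enrolled subject is also the other's household member.

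Patients who decline the study are given a randomised start date as well (Protocol 8.2.4 and 12.1), so a housemate outside the study can bring food into a control's home in the same way.

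**Working it through.** **1. The plan's own figures.** SAP Table 2 gives, for HbA1c after 180 days, mean 8.58, SD 1.74, √(1−R²) 0.66, target effect 10% and required N 55. With two-sided alpha 0.05 (sidedness is not stated, so this is assumed) and 80% power, the multiplier is 1.960 + 0.842 = 2.802.

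- Residual SD = 1.74 × 0.66 = 1.148; effect = 0.858.
- Total N = 4 × (1.148 × 2.802 / 0.858)² = 56.2. This reproduces the stated 55 to within 2.

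The SAP also reports a simulated detectable intention-to-treat effect of 3.7% at N = 500, or 0.037 × 8.58 = 0.317 points. The closed form with the Table 2 SD gives 3.35%. The simulation inputs are not given, so I do not call this an error. The power figures below are calibrated to the SAP's own statement of 80% power at 3.7%.

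**2. Dilution.** Let *s* be the share of subjects who live with one other subject. The documents do not give it; 2 to 10% is assumed. With independent 1:1 assignment half the pairs are split, so the exposed fraction of controls is c = s/2. If the housemate gains the full effect (an upper limit, because only the food is shared), the contrast becomes (1 − c) × effect. Then power = Φ(2.802 × (1 − c) − 1.960), the detectable effect is 3.7% / (1 − c), and the N that restores 80% power is 500 / (1 − c)².

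| s (assumed) | c | exposed controls of 250 | power at 3.7% | detectable effect | N for 80% |
|---|---|---|---|---|---|
| 2% | 1% | 2.5 | 79.2% | 3.74% | 511 |
| 5% | 2.5% | 6.25 | 78.0% | 3.79% | 526 |
| 10% | 5% | 12.5 | 75.9% | 3.89% | 555 |

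**3. 2SLS.** The estimate is the intention-to-treat effect divided by the first stage, and only the numerator changes. At c = 5%, a true full-engagement effect of 5.2% (the SAP's detectable value) would be estimated as 5.2 × 0.95 = 4.94%.

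**4. Timing.** Enrolment is rolling, for up to two years, in random contact order. Assume that two co-residents enrol at independent uniform dates over T months, that treated subjects start at once and that controls start six months later. Let D be the gap between their dates and h = E[max(6 − D, 0)] / 6. For T ≥ 6, h = (2/T²)(3T − 6); for T = 3, h = 1 − (T/3)/6. So h = 0.229, 0.417 and 0.833 for T = 24, 12 and 3.

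The mean exposed fraction of a paired control's six-month window is:

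- **No rule:** ½ × [(½ + ½h) + ½(1 − h)] = 0.50 for every T. Late-starting treated housemates lower it, and earlier-enrolled control housemates who have since started raise it by the same amount. The s/2 figure therefore survives as an average share of control time.
- **Same arm for both:** ½(1 − h) = 0.39, 0.29 and 0.08 for T = 24, 12 and 3.
- **First-randomised subject only, with the housemate entering the program outside the study on an independently randomised start date:** ½h = 0.11, 0.21 and 0.42.

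Giving co-residents the same arm removes most exposure only when they enrol close together. The index rule removes most of it when they enrol far apart, and closes the gap only if the housemate's own program entry does not come before the index control's.

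**The case against.** **Only the food is shared.** Dietitian visits, medication and case management, classes and biometric tracking are described for the participant. This stands: a reader might infer that a control in a split home receives the intervention, and the documents support only its food component.

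**Exposure need not run from the start.** This also stands. If the control enrols first, exposure begins when the housemate starts; if that is more than six months later, the primary window is untouched.

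**Co-enrolment may be rare.** Both people need type 2 diabetes, HbA1c of at least 8.0, no exclusion and consent. Nothing in the documents measures this, so the objection can be neither confirmed nor dismissed. A pilot-sized effect of about one point (Protocol section 6) would be detected with power above 99.9% throughout the assumed range, and the bias is toward zero, so it would not create a spurious benefit.

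**The data already allow checks.** The household identifier permits a count of shared homes, and the SAP plans to compare single- with multi-person households; a person living alone cannot be exposed this way. That is true, but neither document commits to using the identifier for the main analysis. The planned comparison is itself affected, because all the dilution falls in its multi-person group.

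These points limit the size. They do not supply the missing rule.

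**Conclusion.** The gap is in the text: individual assignment, household food, and no rule linking the two. The direction is clear for the intention-to-treat estimate (toward zero), and 2SLS inherits the bias. The size rests on an assumed share of co-resident subjects and on full transfer of the effect through food alone. Under s of 2 to 10% the dilution is at most about 1 to 5%, with power at the stated 3.7% effect falling from 80% to between 79.2% and 75.9%. Food reaching controls through decliners would add to this and cannot be quantified from the documents.

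A reader might go further and infer that the primary comparison is seriously compromised, or that the trial should have been randomised by household throughout. The documents support neither. They give no co-enrolment rate, and the assumed range produces a small loss. This is a cheap improvement to the design and should be made on that footing.

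**What to change.** **Before assignment is revealed.** Add a household check to the REDCap step, using the address on file and the roster of household names and birth dates. The documents do not say whether the roster is taken before the reveal, so that order must be written in. Allow one index (first-randomised) subject per household. Do not randomise as a study subject anyone who lives with a person already enrolled in the program or already assigned a start date, decliners included. Exclusion at this point precedes randomisation and does not bias the comparison.

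**State two things alongside it.** First, one definition of household: the Protocol (9.2.1) uses the subject's roster for the prospective study, while the SAP (3.3) uses addresses. Second, how the program entry of a co-resident outside the study relates in time to the index subject's; the working shows that exposure can persist if this is left open. That timing is for the sponsor to settle.

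**For co-residents already enrolled.** The SAP planned a launch in April 2019 and the Protocol text was approved in February 2020, so some may exist. Use the existing household identifier to cluster standard errors by household, report the number of shared and split homes, and add a sensitivity analysis that excludes controls living with a program participant. Say how relatives in split homes are handled in the spillover analysis.

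**Cost.** One check in the allocation form, a few sentences in each document, and the loss of a few eligible co-residents from the sample.

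**Why not assign co-residents to the same arm.** Besides being only a partial remedy, it overrides the list stratified by HbA1c when the two people fall in different strata. It can also let the second person know the arm before consenting, which Protocol 8.2.1 is meant to prevent.
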